8.7 Clinical Laboratory Evaluations

Blood samples for chemistry, hematology, coagulation, CRP, and procalcitonin will be obtained at Screening, daily from Day 1 through EOT for study drug (Day 5), Day 7, TOC for study drug (Day 12), TOC for BAT, and EOS. Clinical laboratory assessments will be performed post-dose after the second infusion on Day 1. All standard blood tests will be analyzed centrally by a certified clinical laboratory and details on the collection and processing of central laboratory samples can be found in the Laboratory Manual.

Following study drug dosing, the Investigator will review laboratory values for those outside of normal range and will be required to conduct clinically appropriate follow-up procedures. Clinical significance of the values outside of normal ranges will be assessed by the Investigator.

The analytes listed in [Appendix B](#) will be measured at Screening, daily from Day 1 through EOT for study drug (Day 5), Day 7, TOC for study drug (Day 12), TOC for BAT, and EOS.

8.8 Acute Kidney Injury

AKI will be measured at Day 1 and EOS. AKI will be defined as stage 1 or higher using modified RIFLE criteria ([Appendix D](#)) at any time within the first 7 days or new need for renal replacement therapy between Day 1 and EOS.

8.9 Vital Signs

Vital signs will be measured at Screening, prior to infusion (-1 hour window) daily on Day 1 through Day 7, TOC for study drug (Day 12), TOC for BAT, and EOS. Vital signs will include temperature, heart rate, and blood pressure. Vital signs will be obtained at every visit unless the subject has been discharged and visits are being performed remotely. During the Treatment Period, vital signs should be obtained prior to each infusion (-1 hour window). Wherever possible, vital signs will be obtained after at least 5 minutes resting in a supine or sitting position. If more than 1 measurement is taken on a given day, the highest value for temperature should be recorded in the eCRF.

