5.5.2 Study Drug Preparation and Dispensing

5.5.3 Study Drug Administration

AP-SA02 or placebo will be administered via IV bolus infusion every 6 hours for 5 consecutive days in an inpatient location, unless the dose, frequency, or duration is modified after DRC review. For a delayed dosing administration, if the dose is delayed by <2 hours, the original schedule, relative to the first dose of study drug should be kept. If dose administration is delayed by >2 hours, the next dose, and all subsequent doses, should be based on the timing of the delayed dose and subjects should receive all study drug doses, even if this extends the treatment period. Sites should complete dose administration within \pm 30 mins of the scheduled dose administration time. In addition, all subjects will receive at least 14 days (uncomplicated SAB) or 28 days (complicated SAB) and up to 56 days of BAT. BAT will be administered at the discretion of the Investigator.

Subjects must be directly observed during study drug/placebo administration by clinical personnel. The first dose of study drug on Day 1 must occur as close as possible to the time of randomization.

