7.2 Phase 2a Endpoints

The Phase 2a endpoints are the following:

- Time to reach a NEWS2 score ≤ 2 maintained for at least 24 hours or hospital discharge (whichever comes first) for subjects on active drug versus placebo in the Microbiological Intent-to-Treat (MITT) Population;
- Clinical Improvement or response at TOC for study drug (Day 12) in the MITT Population;
- Proportion of subjects reaching a NEWS2 score ≤ 2 maintained for at least 24 hours or hospital discharge (whichever comes first) for subjects on active drug versus placebo at TOC for study drug (Day 12) in the MITT Population;
- Microbiological outcome at EOT for study drug (Day 5);
- Clinical Improvement or response at TOC for BAT (7 days [± 1 day] after the end of BAT);
- Clinical Improvement or response at EOS (28 days after the end of BAT);
- Time to death;
- NEWS2 score while hospitalized by study day;
- Late composite efficacy, as defined by the following:
 - Survival at EOS (Days 39 to 81); and
 - No evidence of microbiological failure, as defined by either of the following:
 - Blood cultures that remain positive for SA ≥ 7 days from randomization; or
 - Isolation of SA from the blood or another sterile site (eg, joint fluid, tissue) > 14 days from randomization.

- Microbiological failure or relapse by any of the following:
 - Blood cultures that remain positive for SA ≥ 7 days from randomization;
 - Isolation of SA from the blood or another sterile site (eg, joint fluid, tissue) >14 days from randomization; or
 - Blood culture positive for SA >72 hours after the first blood cultures showing CL of SAB (defined as 2 consecutive days with negative SA blood cultures).
- Time to resolution of SAB;
- Time to hospital discharge (and time to hospital discharge readiness);
- Need for and duration of intensive care unit stay;
- Need for and duration of endotracheal mechanical ventilation;
- Need for and duration of noninvasive pressure ventilation (eg, Continuous Positive Airway Pressure, Bilevel Positive Airway Pressure);
- PK of AP-SA02 with IV administration;
- Relationship between AP-SA02 exposures and safety and efficacy endpoints;
- Immunogenicity of AP-SA02 at EOS;
- Time to resolution of any signs and/or symptoms of bacteremia present at Screening;
- Time to resolution of any signs/symptoms related to focal site of SA infection (eg, joint pain; redness; swelling; weight-bearing, back pain; weight-bearing, skin redness; drainage) from randomization on Day 1;

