7.3 Efficacy Outcome Assessments

Clinical outcome will be assessed at TOC for study drug, TOC for BAT, and EOS, and will be based on the definitions in Table 2. The signs and symptoms of SAB include the following:

- Documented temperature $\geq 38.0^{\circ}\text{C}$ (100.4°F) or $\leq 36.0^{\circ}\text{C}$ (96.8°F) measured orally, $\geq 38.5^{\circ}\text{C}$ (101.3°F) or $\leq 36.5^{\circ}\text{C}$ (97.7°F) measured tympanically, or $\geq 39^{\circ}\text{C}$ (102.2°F) or $\leq 37^{\circ}\text{C}$ (98.6°F) measured rectally;
- Heart rate >90 beats per minute;
- Respiratory rate >20 breaths per minute;
- White blood cell count $\geq 12.0 \times 10^9$ cells/L or $\leq 0.4 \times 10^9$ cells/L, or $\geq 10\%$ immature neutrophils;
- Systolic blood pressure <90 mmHg; and/or
- Pain associated with focal site of infection.

Note: On Day 7, the Investigator will provide an assessment of whether additional imaging is needed for potential metastatic infection based on clinical signs/symptoms of SA infection.

Table 2. Definition of Clinical Outcome

Clinical Outcome	Definition
Improvement or response (meets all criteria)	
 • The subject is alive; • Eradication of SAB based on blood cultures obtained through Day 7; • No new metastatic foci including and after Day 7 or complications of SAB; and • Resolution of SAB-related clinical signs and symptoms that were present at baseline.
No response (meets 1 or more criteria)	
 • Death due to any cause; • Persistence of bacteremia based on blood cultures obtained through Day 7 or recurrence of SAB; • Development of new metastatic foci after Day 7 or other complications related to SA; or • Persistence, worsening, or recurrence of attributable signs and symptoms of SAB which were present at baseline.
Indeterminate	Study data not available for the evaluation of efficacy due to lost to follow-up, withdrawal of consent, or missing data.

SA = *Staphylococcus aureus*; SAB = *Staphylococcus aureus* bacteremia.

7.4 National Early Warning Score 2

Table 3 presents the NEWS2 scoring system. A NEWS2 score will be recorded once per day (and should be repeated if there is a change in clinical status) from Day 1 through Day 7 and TOC for study drug (Day 12). NEWS2 is an aggregate scoring system derived from 6 physiologic parameters:

- Respiration rate;
- Oxygen saturation;
- Systolic blood pressure;
- Pulse rate;

- Level of consciousness or new confusion; and

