If Day 12 blood culture is positive, the subject will not be considered have initial resolution of SAB although there may be 2 or more consecutive negative blood cultures before Day 12. If EOS or BAT blood culture is positive, the subject will be considered as initial resolution of SAB when there are 2 or more consecutive negative blood cultures before EOS or BAT, and the initial resolution date and time will be the first date and time with 2 consecutive negative blood cultures. The subjects who do not experience the resolution will be censored at the last collection date and time of blood culture.

- Time to initial resolution of SAB (days) = (Censoring date and time/first date and time of 2 consecutive days with negative SA blood culture – date and time of first dose of study drug) /3600/24

The Kaplan-Meier method will be used to estimate the 25%, median and 75% times. The hazard ratio, 95% confidence interval (CI) of hazard ratio, and p-value from Cox regression model will be provided to compare AP-SA02 and placebo. Cox regression will include treatment (AP-SA02 and placebo) as factor.

The Kaplan-Meier plot of time to initial resolution of SAB will be provided.

Time to resolution of any signs and/or symptoms of bacteremia present at Screening will be analyzed using the Kaplan-Meier method as other time-to-event endpoints.

- Time to resolution of signs/symptoms of bacteremia (days) = Censoring date/date of first resolution of any signs/symptoms of bacteremia - date of first dose of study drug + 1

The Kaplan-Meier method will be used to estimate the 25%, median and 75% times. The hazard ratio, 95% confidence interval (CI) of hazard ratio, and p-value from Cox regression model will be provided to compare AP-SA02 and placebo. Cox regression will include treatment (AP-SA02 and placebo) as factor.

The Kaplan-Meier plot of time to resolution of any signs and/or symptoms of bacteremia present at Screening will be provided.

The signs and symptoms of SAB will be determined programmatically based on the following:

- Documented temperature  $\geq 38.0^{\circ}\text{C}$  ( $100.4^{\circ}\text{F}$ ) or  $\leq 36.0^{\circ}\text{C}$  ( $96.8^{\circ}\text{F}$ ) measured orally,  $\geq 38.5^{\circ}\text{C}$  ( $101.3^{\circ}\text{F}$ ) or  $\leq 36.5^{\circ}\text{C}$  ( $97.7^{\circ}\text{F}$ ) measured tympanically, or  $\geq 39^{\circ}\text{C}$  ( $102.2^{\circ}\text{F}$ ) or  $\leq 37^{\circ}\text{C}$  ( $98.6^{\circ}\text{F}$ ) measured rectally;

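### Recording only the day's highest temperature can hide a low-temperature sign of bacteremia and date its resolution too early

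*Protocol*

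**What the plan says.** **Recording.** Protocol 8.9, and footnote n of Appendix A in both the Protocol and the SAP, give one rule: "If more than 1 measurement is taken on a given day, the highest value for temperature should be recorded in the eCRF". It has no counterpart for the lowest value, does not mention route and is not limited to particular visits.

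**Number of readings.** Protocol 8.9 and footnote o ask for vital signs before every infusion in the treatment period. Under Protocol 5.5.3 study drug is "administered via IV bolus infusion every 6 hours for 5 consecutive days in an inpatient location", unless changed after DRC review. That makes about four temperatures a day on Days 1-5.

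**The sign.** Protocol 7.3 and SAP 3.6 define the temperature sign on both sides. Low is at or below 36.0 C oral, 36.5 C tympanic or 37 C rectal. High is at or above 38.0, 38.5 or 39 C respectively.

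**Its use.** Protocol 7.2 lists the endpoint "Time to resolution of any signs and/or symptoms of bacteremia present at Screening". SAP 3.6 says "The signs and symptoms of SAB will be determined programmatically based on the following", and the event time is "date of first resolution of any signs/symptoms of bacteremia - date of first dose of study drug + 1". Clinical Improvement or response (Protocol 7.3, Table 2) also requires "Resolution of SAB-related clinical signs and symptoms that were present at baseline", but SAP 3.4.1 has the investigator and the CEAC assess it. SAP 3.7.3 summarises the minimum post-baseline temperature.

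**The concern.** A recording rule that looks only upward feeds a criterion that looks both ways. For fever, keeping the maximum is conservative, because any febrile reading survives. For low temperature it does the reverse: one reading above the cut-off removes every low reading of that day from the database.

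Three consequences follow.

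- **Event date.** The endpoint is dated at first resolution and SAP 3.6 does not require it to be sustained, so one masked day is enough to clear the temperature component. If all signs must be absent together, the others must also be absent that day.
- **Baseline.** If several temperatures are taken on a Screening day, a low one can be dropped in the same way, and the sign never enters the set that has to resolve.
- **Safety summary.** On days with several readings, the minimum temperature in SAP 3.7.3 becomes the lowest of the daily maxima.

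Readings that never reach the eCRF can be recovered only by going back to source records.

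**Working it through.** The plan gives no figure on this point to reproduce. The check applies the rule to the sign definition and then shows how the size varies under stated assumptions.

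**1. Worked days (oral cut-off 36.0 C, four readings)**

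| Readings (C) | Recorded | Low sign by program | Readings at or below 36.0 |
|---|---|---|---|
| 35.6, 35.8, 36.2, 35.7 | 36.2 | absent | 3 of 4 |
| 35.6, 35.8, 35.9, 35.7 | 35.9 | present | 4 of 4 |

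The first day can count as resolved although three of four readings were low. The second shows the limit: if every reading is low, the maximum is low too, and nothing is hidden. Masking needs a mixed day.

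**2. General formula.** Let k be the readings per day and q the chance that one reading is at or below the cut-off, with readings independent (assumptions).

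- At least one low reading: 1 - (1 - q)^k
- Recorded maximum is low: q^k
- Masked share of days with a low reading: [1 - (1 - q)^k - q^k] / [1 - (1 - q)^k]

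With k = 4 and q = 0.75: at least one low reading = 1 - 0.25^4 = 0.996; maximum low = 0.75^4 = 0.316; masked share = (0.996 - 0.316)/0.996 = 68%. By the same formula it is 93% at q = 0.5, 34% at q = 0.9 and 0% at q = 1.

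**3. In terms of temperature.** Four normal readings a day were simulated, independent around the day's mean and rounded to 0.1 C. Means and SDs are assumptions; the documents give none. Masked share of days with a low reading:

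| Day mean (C) | SD 0.2 | SD 0.3 | SD 0.5 |
|---|---|---|---|
| 35.2 | 0% | 1% | 17% |
| 35.5 | 1% | 13% | 44% |
| 35.7 | 15% | 40% | 67% |
| 35.9 | 64% | 77% | 85% |

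Masking is rare when the subject is clearly cold and common when the mean is just under the cut-off.

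**4. After the change.** If the lowest value is also recorded and the low limb is read from it, the masked share is 0% for any q.

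**5. Price of reading the low limb from the minimum.** Take an assumed recovered oral mean of 36.6 C and SD 0.4 C, unrounded. Then q = P(Z <= -1.5) = 0.067, and at least one low reading occurs on 1 - 0.933^4 = 24% of days. At an assumed mean of 36.8 C it is 9%. An any-reading flag for every subject would therefore mark recovered people as still having the sign. This is why the fix is limited to subjects whose baseline sign was low temperature.

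**The case against.** A reader might infer that hypothermia is always recorded as resolved while it persists. The documents do not support that: a day on which all readings are low is still recorded as low. With an assumed mean of 35.5 C and SD of 0.4 C, unrounded, q = 0.894 and the recorded maximum is still low on 0.894^4 = 64% of days. Positive correlation between readings on the same day would make mixed days rarer still.

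A reader might also infer that Clinical Improvement or response, on which the power statement rests, is compromised. That link is weak. The investigator and the CEAC assess it, and nothing confines the investigator to one eCRF value. SAP 3.4.1 reports it at Day 12, TOC for BAT and EOS, where no repeated daily readings are scheduled.

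Nor do the documents show a bias between arms: the rule is the same in both, under blinding. Temperature is one of six listed signs, and the number of subjects who qualify by its low limb is not given. Protocol 9.2.1 and SAP 3.1.4 plan no formal testing, although SAP 3.6 reports a hazard ratio and p-value for this endpoint.

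Other temperature data may exist. NEWS2 parameters are entered in the eCRF, and SAP 3.7.3 mentions average values per visit. The documents do not say whether the highest-value rule governs the NEWS2 entry. Finally, no section says that one subject is measured by different routes on the same day, so loss of an abnormal reading through mixed routes is possible but speculative.

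These points limit the size and reach of the problem. They do not remove it: no section captures the lowest value, and SAP 3.6 derives a two-sided sign by program.

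**Conclusion.** The mismatch is real and sits in current text. On dosing days with mixed readings, a low-temperature sign can be recorded as absent and counted as first resolution in the time-to-resolution endpoint of SAP 3.6. Low temperature at Screening can be missed in the same way, and the SAP's minimum temperature is affected.

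For assumed means of 35.5 to 35.9 C and SDs of 0.2 to 0.5 C, with independent oral readings, masking affects about 1% to 85% of days with a low reading. The high end applies only near the cut-off. What is shown is misclassification and early event dates on mainly one descriptive endpoint. The effect on the trial's results cannot be sized without the number of subjects who qualify by low temperature. The change is worth making because it is cheap and the lost readings are hard to recover later.

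**What to change.** - **Protocol 8.9 and footnote n of both appendices:** record the highest and the lowest temperature of the day, or all readings, each with its route. State whether this also governs the NEWS2 temperature entry.
- **SAP 3.6:** for subjects whose baseline sign was low temperature, assess resolution of that limb on the lowest recorded value against the existing cut-off for its route. Keep the highest value for the fever limb. Do not apply an any-reading flag to all subjects.

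**Cost.** One or two extra eCRF fields and a few sentences, with no extra measurement. Some subjects with a low baseline sign and normal-low readings afterwards will get later resolution dates.

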8.10 Electrocardiogram

A 12-lead ECG will be conducted at Screening, post first dose on Day 1, Day 3, EOT for study drug (Day 5), TOC for study drug (Day 12), TOC for BAT, and EOS. The Investigator will evaluate ECGs for abnormal results and document the clinical significance of these, reporting as AEs or medical history where appropriate.

8.11 Physical Examination

A complete physical examination will be performed at Screening, Day 7, TOC for study drug (Day 12), TOC for BAT, and EOS. A targeted physical examination will be performed daily from Day 1 through Day 6.

A complete physical examination will include evaluation of head, eyes, ears, nose, and throat (HEENT), neck, lungs, heart, chest, abdomen, extremities, neurologic status, skin for evidence of emboli, palpation for signs of pain, and any other notable conditions. A targeted physical examination will include evaluation for complications of bacteremia, HEENT, lungs, heart, skin for any evidence of septic emboli, and palpation for signs of pain. Pain on a physical examination should trigger diagnostic testing for metastatic foci of infection.

9 STATISTICS

9.1 Analysis Populations

The following analysis populations will be defined for the Phase 1b and Phase 2a cohorts:

- Intent-to-Treat (ITT): all randomized subjects regardless of whether or not study drug is received;
- Phage-Sensitive ITT: all randomized subjects who receive both BAT and study drug, and whose SA isolate is sensitive to at least 1 of the phage components that comprise the study drug;
- Safety: all randomized subjects who receive at least 1 dose of study drug;
- MITT: all subjects in the ITT Population with baseline SAB and who receive at least 1 dose of study drug; and
- PK: all subjects (enrolled at predetermined/qualified PK sites) who have at least 1 PK sample drawn.

An SAP will be prepared and finalized before database lock and analyses of data. Summary data will be tabulated and presented by treatment group.

9.2 Statistical Methods

Predefined or post-hoc statistical analysis for all subjects may be performed to compare the treatment groups that are randomized based on the following:

- MRSA subjects (subgroup will be for Phase 2a only);
- Blood cultures positive for SA on Day -1 prior to study drug administration; and
- Source control achieved (eg, abscess drainage, catheter or intravascular device removal, washout of infected joint).

Note: The final SAP will finalize the subgroup analyses.

9.2.1 Analysis of Phase 2a Endpoints

Phase 2a endpoints will be summarized descriptively for each treatment arm using appropriate proportions and means depending on the data type along with the 95% confidence interval. No formal hypothesis testing is planned.

Additional details will be described in the SAP.

9.2.2 Analysis of Safety

Safety will be assessed by monitoring AEs, vital signs, laboratory data (chemistries, hematology, and coagulation), immunogenicity evaluation, physical examinations, ECGs, and radiologic imaging per standard of care (eg, echocardiogram).

9.2.3 Analysis of Pharmacokinetics

PK samples for AP-SA02 will be collected from subjects enrolled at predetermined/qualified PK sites per protocol and evaluated based on AP-SA02 levels as measured by venous blood samples.

PK parameters of AP-SA02 will be assessed from subjects enrolled at predetermined/qualified PK sites with serial PK sampling, including C_{max} , T_{max} , $t_{1/2}$, CL , V_z , AUC_{0-t} , and $AUC_{0-\infty}$. Additional details regarding PK analysis methodology will be described in the SAP.

9.2.4 Analysis of Pharmacodynamics

Pharmacodynamics will be evaluated based on the following:

- Time to resolution of signs/symptoms of bacteremia present at Screening;
- Time to resolution of bacteremia based on blood cultures; and/or
- Change in CRP from baseline.

9.2.5 Clinical Efficacy Adjudication Committee

The Clinical Efficacy Adjudication Committee (CEAC) will consist of a group of independent clinical experts blinded to treatment allocation and not associated with study conduct. Data obtained for subjects who receive study drug may be reviewed independently by CEAC members. The CEAC members will give their opinion on the diagnosis and classification of the SAB, the adequacy of BAT, the adequacy of source control, and/or the response assessment (overall success or failure). For deaths occurring during the study, a blinded assessment of the attribution of death to SAB or to another cause may be performed by the CEAC members.

9.2.6 Sample Size Determination

The study will enroll approximately 50 eligible subjects. Enrollment may be expanded up to a total of approximately 100 subjects to ensure that at least 8 treated and 4 placebo Phase 2a subjects are MRSA subjects and to account for additional subjects and cohorts that may be enrolled based on DRC review and Sponsor input based on emerging data. To ensure that at least 8 treated and 4 placebo Phase 2a subjects are MRSA subjects, no more than approximately 70 non-MRSA subjects will be enrolled without a protocol amendment.

The Phase 1b MAD safety cohorts will follow a standard 3 + 1 design for 2 cohorts ($n = 4$ for each cohort for a total of 8 subjects). However, additional cohorts (up to 3) may be added or existing cohorts expanded per recommendation of the DRC or Sponsor decision. The total sample size in Phase 1b may be increased up to a total of 20 subjects without a protocol amendment in consultation with the DRC.

Phase 2a will have an initial sample size of approximately $n = 42$ with a study drug to placebo allocation of 2:1 in order to enroll at least 38 subjects meeting the MITT Population criteria with the assumption that approximately 90% of randomized subjects will satisfy the MITT Population criteria. This will provide at least 80% power to detect a difference of 50% in the proportion of subjects in each treatment arm, with a 30% placebo portion meeting all conditions for Clinical Improvement or response at TOC for study drug (Day 12) in the MITT Population with a type 1 error rate of 0.05 (1-sided) using Fisher's exact test. Additional subjects may be included in Phase 2a after a protocol amendment.

